## 15.0 Community-Based Participatory Research

15.1 *Describe involvement of the community in the design and conduct of the research.*

*NOTE: Community-Based Participatory Research (CBPR) is a collaborative approach to research that equitably involves all partners in the research process and recognizes the unique strengths that each brings. CBPR begins with a research topic of importance to the community, has the aim of combining knowledge with action and achieving social change to improve health outcomes and eliminate health disparities.*

Response:

- ☒ N/A: This study does not utilize CBPR.

15.2 *Describe the composition and involvement of a community advisory board.*

Response:

- ☒ N/A: This study does not have a community advisory board.

## 16.0 Resources and Qualifications

16.1 *Describe the qualifications (e.g., education, training, experience, expertise, or certifications) of the Principal Investigator **and** staff to perform the*

*research. When applicable describe their knowledge of the local study sites, culture, and society. Provide enough information to convince the IRB that you have qualified staff for the proposed research.*

*NOTE: If you specify a person by name, a change to that person will require prior approval by the IRB. If you specify a person by role (e.g., coordinator, research assistant, co-investigator, or pharmacist), a change to that person will not usually require prior approval by the IRB, provided that the person meets the qualifications described to fulfill their roles.*

Response: The PI, [name] is a Professor of Neurology at UB and a Movement Disorder specialist with 22 years of caring for PD patients. [name] has served as PI on 9, hypothesis-driven clinical trials and site-PI on 3, industry-sponsored clinical trials. [name] is an Assistant Professor of Neurology at UB and a Movement Disorder specialist with 3 years of caring for PD patients. The study coordinator has over 10 years of experience in this role on clinical trials.

***Describe other resources available to conduct the research.***

***16.2 Describe the time and effort that the Principal Investigator and research staff will devote to conducting and completing the research.***

*NOTE: Examples include the percentage of Full Time Equivalents (FTE), hours per week. The question will elicit whether there are appropriate resources to conduct the research.*

Response: The PI will devote 0.2FTE and the coordinator 0.2FTE towards this project.

***16.3 Describe the availability of medical or psychological resources that subjects might need as a result of anticipated consequences of the human research, if applicable.***

*NOTE: One example includes: on-call availability of a counselor or psychologist for a study that screens subjects for depression.*

Response: N/A

***16.4 Describe your process to ensure that all persons assisting with the research are adequately informed about the protocol, the research procedures, and their duties and functions.***

Response: The PI will directly communicate with all study staff to review study procedures and define each member's duties. The PI will monitor all staff throughout the study to ensure that study procedures are being followed appropriately.

## **17.0 Other Approvals**

17.1 Describe any approvals that will be obtained prior to commencing the research (e.g., school, external site, funding agency, laboratory, radiation safety, or biosafety).

Response:

☐ N/A: This study does not require any other approvals.

## 18.0 Provisions to Protect the Privacy Interests of Subjects

18.1 Describe how you will protect subjects' privacy interests during the course of this research.

*NOTE: Privacy refers to an individual's right to control access to him or herself. Privacy applies to the person. Confidentiality refers to how data collected about individuals for the research will be protected by the researcher from release. Confidentiality applies to the data.*

*Examples of appropriate responses include: "participant only meets with a study coordinator in a classroom setting where no one can overhear", or "the participant is reminded that they are free to refuse to answer any questions that they do not feel comfortable answering."*

Response: Study subjects will meet with either the PI or coordinator in a clinic room with the door shut for privacy.

18.2 Indicate how the research team is permitted to access any sources of information about the subjects.

*NOTE: Examples of appropriate responses include: school permission for review of records, consent of the subject, HIPAA waiver. This question **does apply** to records reviews.*

Response: Consent of the subject.

## 19.0 Data Management and Analysis\*

19.1 Describe the data analysis plan, including any statistical procedures. This section applies to both quantitative and qualitative analysis.

Response: Given the proof-of-concept nature of the proposed study there is not a single primary outcome but rather treatment groups will be compared with regards to multiple outcomes in a primary fashion. While there are tests of several outcomes being carried forth, which will inflate the experiment-wise error rate to be greater than the specified nominal level of 0.05, it is reasonable to expect these tests to be highly correlated. Hence, given we are in the preliminary phase of our investigation, no adjustments for multiple tests across outcomes will be made. Standard adjustments for multiple testing for a given outcome will still be implemented.

Missing data:

The amount and nature of missing data will be characterized and no method of imputation will be used for missing data. A summary of missing data will be provided according to the number of subjects and the time points where the data are missing. We acknowledge the possibility of informative missingness, that is, the probability of a particular observation being missing may be related to the health of a subject, and therefore analyses will be interpreted with caution.

**Descriptive analyses:**

Measured outcome variables will be summarized overall and by relevant demographic and baseline variables. Descriptive statistics such as frequencies and relative frequencies will be computed for all categorical variables. Numeric variables will be summarized using simple descriptive statistics such as the mean, standard deviation and range. A variety of graphical techniques will also be used to display data, ex., histograms, boxplots, scatterplots, etc. MRI data will be processed and analyzed by the Buffalo Neuroimaging Analysis Center (BNAC) under the direction of [name].

**Statistical analyses:**

All statistical analyses of outcomes at each time point will be performed using identical methodologies. The statistical assessment of each considered outcome will be based on a standard analysis of variance (ANOVA) model. In this case, each outcome will be fit as a function of randomized group assignment, baseline cognition, and the interaction between group assignment and baseline cognition. Rather than utilizing the null distribution associated with the classic tests for treatment differences within the ANOVA framework which is dependent on the validity of distributional assumptions, an exact permutation testing approach will be utilized. The randomization mechanism at work is a crucial component in this study in that it will be used to create the randomization distribution by which statistical significance will be determined. Reported p-values will be obtained from the permutation distributions of the test statistics based on 10,000 Monte Carlo simulations. All possible pairwise comparisons will be made between the three treatment groups in conjunction with a Bonferroni adjustment for multiple comparisons performed at a 0.05 family-wise error rate. All statistical tests will be two-sided. In addition, since the comparability of treatment groups may be questioned due to chance imbalance in confounding variables, covariates will be added to the above models as a series of secondary analyses. The interaction of patient covariates and randomized assignment will be examined so to assist in the identification of patient subgroups of interest. All adverse events will be recorded during the study period and then tabulated at the end of the study along with the results of the physical exams. All available data from subjects who fail to complete this study will be included in the safety summaries. The probability of an adverse event will be estimated for each treatment group along with the 95% exact confidence interval based on the method of Clopper and Pearson. All analyses will be carried out using SAS version 9.4 (or higher) statistical software (Cary, NC).

*19.2 If applicable, provide a power analysis.*

*NOTE: This may not apply to certain types of studies, including chart/records reviews, survey studies, or observational studies. This question is asked to elicit*

*whether the investigator has an adequate sample size to achieve the study objectives and justify a conclusion.*

Response: N/A

*19.3 Describe any procedures that will be used for quality control of collected data.*

Response: N/A

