## 5.0 Study Design\*

*5.1 Describe and explain the study design (e.g. case-control, cross-sectional, ethnographic, experimental, interventional, longitudinal, observational).*

Response:

We will enroll 15 additional PD patients within five months. Eligible patients will have PD for <4 years diagnosed by a movement disorder specialist (Drs. [name] or [name]), be 45-80 years old, have normal thyroid and renal function at the screening visit, have no previous exposure to lithium therapy, have no history of brain surgery, have no hx of brain imaging findings suggesting another neurological condition besides PD, have no use of tobacco or THC products for >1 year, have stable PD medications for >30 days without current need for adjustments in the investigator's opinion, and have stable psychiatric and diuretic medications for >60 days with no anticipated need for changes for at least 24 weeks.

All patients will receive medium-dose lithium aspartate therapy (30-45mg/day) for 24 weeks ensuring that the study will be completed within 12 months. The following dose titration will be used in order to minimize side effects: 10mg bid x 1 week, then 15mg bid x 1 week, then 20mg bid x 2 weeks, then 20mg qAM and 25mg qhs thereafter. Patients will be contacted weekly over the first 4-6 weeks to assess for side effects that are likely to be due to lithium, such as sedation, dizziness or confusion. If side effects occur and are bothersome to the patient, the dose will be decreased incrementally to a minimum of 30mg/day. Such a design will enable identification of the maximum tolerated dose for study in a future trial and maximize the number of patients receiving the most promising dose (45mg/day) identified in the previous pilot clinical trial. Blood-based biomarkers and MRIs will be assessed at baseline and 24 weeks.

The primary blood-based biomarker outcome measure will be change in PBMC Nurr1 mRNA expression from baseline to 24 weeks, which will be compared with the data from the three control PD patients from the pilot study using ANCOVA. PBMC mRNA expression will be assessed by quantitative real-time PCR using TaqMan probes to match the pilot study's methodology. Based on the

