22% standard deviation among the three control patients and the 540% treatment effect size for the primary outcome from the pilot study results, only two patients would be needed to detect a difference with 95% power at a 2-tailed alpha of 0.05. Secondary outcome measures will include 24-week changes in PBMC SOD-1 expression, PBMC pS9/total glycogen synthase kinase-3B (GSK-3B) and pThr308, pS473 and t-Akt and plasma interleukin-6 (IL-6) levels. Blood-based biomarkers will be assessed by [name]. Statistical analyses will be performed by [name].

The primary MRI outcomes will be 24-week MRI changes in DMN-T, nbM and pSN FW. Using ANCOVA, these outcomes will be compared with the known natural history of such changes in PD derived from the UF and PPMI longitudinal cohorts summarized in Table 1. In addition, secondary comparisons will be made between changes in these lithium-treated patients and age-matched and disease-duration-matched PD subsets from PPMI.

Exploratory clinical outcomes will include changes in Movement Disorder Society-Unified Parkinson's Disease Rating Scale (MDS-UPDRS) Part III (Motor Examination) with subjects in the "on" state, Montreal Cognitive Assessment (MoCA), Parkinson's Anxiety Scale, Geriatric Depression Scale-15, Fatigue Severity Scale, Insomnia Severity Index and Parkinson's Disease Questionnaire-8. Adverse events and medication compliance will be assessed at a three month phone call. Trough serum lithium and safety labs including HgA1C will be assessed at each visit. Because both baseline and on-treatment lithium levels will mostly be below the level of detection using conventional clinical laboratory services (i.e. Kaleida or Quest), these assays will be performed by the UB Chemistry Instrument Center under the direction of [name]. A protocol was developed by Drs. [name] and [name] for these assays for the pilot study that provided reliable results able to detect baseline lithium levels in all patients prior to initiation of lithium therapy.

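### Sections 5.1 and 19.1 give different primary models, and neither names the outcome's own baseline as a covariate

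*Combined protocol and SAP*

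**What the plan says.** Section 19.1 (Statistical analyses) contains the only fully written model. It opens with "All statistical analyses of outcomes at each time point will be performed using identical methodologies" and continues: "each outcome will be fit as a function of randomized group assignment, baseline cognition, and the interaction between group assignment and baseline cognition". The comparisons are then set out as "All possible pairwise comparisons will be made between the three treatment groups". Other adjustment is left to later models: "covariates will be added to the above models as a series of secondary analyses". Those covariates are not named.

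Section 5.1 (Study Design) describes the primary outcomes differently. For blood: "The primary blood-based biomarker outcome measure will be change in PBMC Nurr1 mRNA expression from baseline to 24 weeks". The comparator and method for that blood outcome are then given in these terms: "which will be compared with the data from the three control PD patients from the pilot study using ANCOVA". For imaging: "The primary MRI outcomes will be 24-week MRI changes in DMN-T, nbM and pSN FW". The imaging comparator and method, in turn, are given in these terms: "Using ANCOVA, these outcomes will be compared with the known natural history of such changes in PD derived from the UF and PPMI longitudinal cohorts". No covariate is listed for either ANCOVA.

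The baseline values exist. Sections 3.0 and 12.1 schedule the blood targets, MRI, MDS-UPDRS Part III and questionnaires at baseline and Week 24, and MoCA at screening and Week 24. Section 5.1 also says that the PCR method will follow the pilot's, so Nurr1 in the new patients and in the pilot controls should be on the same footing.

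**The concern.** An analyst following 19.1 literally could fit Week 24 levels with cognition as the only baseline term. An analyst following 5.1 would fit changes by ANCOVA and would have to choose the covariates. The two would report different estimates for the same primary outcome, in an open-label study with no rule for which one counts.

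The baseline measurement is usually the best predictor of the Week 24 measurement, and the plan does not say that it will be used. Baseline cognition takes its place even for mRNA in blood cells, where the documents give no reason to expect it to be prognostic. At stake for Nurr1 is how much of any starting difference between 15 treated patients and three controls ends up in the estimated effect, and how wide its interval is. Replacing the three-group wording in 19.1 with lithium versus control would leave this open.

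**Working it through.** **The plan's own figure first.** Section 5.1 gives an SD of 22% and an effect of 540% (679 − 139 from the pilot), and concludes that two patients suffice for 95% power at two-sided 0.05. The usual formula gives n per group = 2 × [22 × (1.960 + 1.645) / 540]² = 0.043, which rounds up to 1. A two-sample t-test with two per group has power above 0.999. The stated two is therefore reproduced as a practical minimum. It is computed on percent change, not on a Week 24 level, and does not depend on the point made here.

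**Inputs for the check.** 15 treated and three controls (section 5.1). The correlation rho is not in the documents, so 0.3 to 0.9 is shown. Assumptions: equal SD in both groups and at both times, additive change, and baseline gaps that arise by chance.

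**Size of a chance baseline gap.** Its SD is √(1/15 + 1/3) = 0.632 outcome SDs. The probability that it exceeds 0.5 SD in either direction is 43%, and 1 SD, 11%.

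**What a gap does to the estimate, per 1 SD of gap.**
- Week 24 value: +rho.
- Change without baseline adjustment: rho − 1 (regression to the mean).
- Own-baseline ANCOVA: zero in expectation.

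**Precision.** The SE in SD units is 0.632 × √1 for the value, 0.632 × √(2(1 − rho)) for the change, and 0.632 × √(1 − rho²) for own-baseline ANCOVA.

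| rho | SE value | SE change | SE ANCOVA | Variance saved by ANCOVA v value | v change | Carried in per 1 SD gap: value | change |
|---|---|---|---|---|---|---|---|
| 0.3 | 0.632 | 0.748 | 0.603 | 9% | 35% | +0.3 | −0.7 |
| 0.5 | 0.632 | 0.632 | 0.548 | 25% | 25% | +0.5 | −0.5 |
| 0.7 | 0.632 | 0.490 | 0.452 | 49% | 15% | +0.7 | −0.3 |
| 0.9 | 0.632 | 0.283 | 0.276 | 81% | 5% | +0.9 | −0.1 |

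The ratio of ANCOVA to change variance is (1 + rho)/2, which is below 1 for any rho below 1. The change score beats the Week 24 value only when rho exceeds 0.5.

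**Small-sample check.** These formulas ignore the cost of estimating a slope from 18 patients. A simulation of 6,000 runs, with one covariate fitted in every model and the interaction left out, gave an SE of 0.65 for the value with an unrelated covariate. At rho 0.5, 0.7 and 0.9 it gave 0.65, 0.51 and 0.29 for change with an unrelated covariate, and 0.56, 0.47 and 0.28 for own-baseline ANCOVA. The ordering holds. Since 19.1 already spends a term on cognition, swapping that term costs no extra degree of freedom.

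**The case against.** The strongest reply is that the two sections can be read together: 5.1 says what the outcome is, 19.1 says how to model it, and so the outcome in 19.1 is already the change. The wording about time points may be left over from the design that still had a Week 12 visit, which Revision 2 removed. This has force. A reader might infer that 19.1 analyses raw Week 24 values, never uses baseline, and so counts pre-treatment differences as lithium effect. The documents do not support that. 19.1 is silent on value or change, 5.1 specifies change, its ANCOVA covariates are simply unlisted, and secondary models may add covariates. For MoCA, the only cognitive test scheduled, baseline cognition would presumably be the outcome's own baseline.

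A reader might also infer a large loss of power. In the simulation above, for an assumed effect of 1.5 SD, the value-only model has 58% power, against 69%, 85% and over 99% for own-baseline ANCOVA at rho 0.5, 0.7 and 0.9. That contrast should not be used. It omits the written interaction and permutation test, takes its effect size from outside the documents, and leaves out 5.1's change score, which reaches 58%, 79% and over 99%. Against that, the gain is about 11, 6 and 0 points. On the plan's own Nurr1 inputs (540/22, about 25 SD), precision would not be limiting at all, although that SD comes from three patients.

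Two further points stand. The three controls are the comparator for Nurr1 only; free water is compared with the UF and PPMI cohorts. And section 4.1 links DMN-T and nbM free water to cognitive decline, so cognition is not irrelevant to every outcome.

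Reading the sections together still does not settle the covariate. Change alone leaves the regression-to-the-mean term, and unnamed secondary covariates do not alter the primary model.

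**Conclusion.** The concern holds as a conflict and an omission. Sections 5.1 and 19.1 specify different primary models, and neither states that the outcome's own baseline is a covariate. It does not hold as a demonstrated bias in the lithium effect.

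The practical size is bounded by the table. Relative to a literal Week 24 analysis, own-baseline ANCOVA removes 9% to 81% of the variance as rho runs from 0.3 to 0.9. Relative to section 5.1's change score it removes 35% down to 5%, so the gain there is modest when rho is high. These figures rest on an assumed rho, equal variances and the 15 versus 3 Nurr1 comparison. They do not describe the MRI comparison.

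The 0.63 SD gap is what chance alone would give. The controls come from the earlier pilot, so a real gap may be systematic. Change and ANCOVA can then answer different questions, and neither makes the comparison randomised.

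**What to change.** In section 19.1, replace the outcome and covariate wording with one model that agrees with 5.1:

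- **Outcome:** change from baseline to Week 24 (screening to Week 24 for MoCA), with the scale stated, since the pilot Nurr1 results are given as percent change.
- **Covariate:** that outcome's own baseline in place of baseline cognition, wherever individual comparator data measured by the same method exist. Nurr1 against the pilot controls is the clear case. On an additive scale, modelling the change or the Week 24 value then gives the same group estimate.
- **MRI against UF and PPMI:** keep 5.1's change score without a pooled baseline covariate. Acknowledge that if rho is below 0.5 a change score is less precise than the Week 24 value.
- **Cognition:** secondary model only.
- **Limitation:** state that baseline adjustment does not make the comparison with non-concurrent controls randomised.

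List the same covariates beside the ANCOVA statements in 5.1. The cost is wording only: no extra visits, assays or patients. It should be settled before Week 24 results are examined.

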### Eligibility Criteria:

1. Diagnosed with PD according to the UK Brain Bank Criteria within the past four years with Hoehn & Yahr stage 1 or 2.
2. 45-80yo.
3. Stable PD medications for previous 30 days and no current need for changes in the opinion of the PI.
4. No formed visual hallucinations or delusions for previous year.
5. Screening MoCA  $\geq 20$ .
6. Never taken prescription or over-the-counter lithium.
7. Stable doses of antidepressants, antihypertensives, diuretics and non-steroidal anti-inflammatory medications (NSAIDs) for previous 60 days and no current need to adjust such medications.
8. No history of cardiac arrhythmias besides atrial fibrillation that is rate controlled.
9. No unstable cardiac, medical, neurologic or psychiatric condition in the opinion of the PI.
10. No current use of illicit drugs or current alcohol abuse in the opinion of the PI.
11. Normal thyroid stimulating hormone (TSH) level at screening visit.
12. Estimated renal glomerular filtration rate  $\geq 50$  at screening visit.
13. No history of receiving or planning to receive nilotinib or a glucagon-like peptide-1 agonist medication such as exenatide.
14. No use of tobacco, THC or CBD products for the previous year.
15. No history of brain surgery or possible need for brain surgery including deep brain stimulation (DBS) for at least 1-year in the opinion of the PI.
16. Women with child bearing potential will need a negative pregnancy test and not be nursing an infant at screening. Women with child bearing potential will need to report using barrier method or hormonal contraception.
17. Not enrolled in another clinical trial.
18. Willing and able to sign informed consent and follow study procedures.

8.2 Describe the criteria that define who will be **excluded** from your final study sample.

NOTE: This may be done in bullet point fashion.

Response:

See 8.1.

8.3 Indicate specifically whether you will include any of the following special populations in your study using the checkboxes below.

**NOTE: Members of special populations may not be targeted for enrollment in your study unless you indicate this in your inclusion criteria.**

Response:

- ☐ Adults unable to consent
- ☐ Individuals who are not yet adults (infants, children, teenagers)
- ☐ Pregnant women
- ☐ Prisoners

**8.4** *Indicate whether you will include non-English speaking individuals in your study. **Provide justification if you will exclude non-English speaking individuals.***

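### Section 19.1 puts a group-by-baseline-cognition interaction in the main model for every outcome without saying at which cognition value the groups are compared; power depends heavily on that choice

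*Combined protocol and SAP*

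**What the plan says.** Section 19.1 (Statistical analyses) is the only place that lists model terms, and it applies them to all outcomes: "each outcome will be fit as a function of randomized group assignment, baseline cognition, and the interaction between group assignment and baseline cognition". Treatment differences are then tested by permutation: "Reported p-values will be obtained from the permutation distributions of the test statistics based on 10,000 Monte Carlo simulations". Tests are two-sided, and "All possible pairwise comparisons will be made between the three treatment groups in conjunction with a Bonferroni adjustment" is planned at a family-wise 0.05. On software it says only that "All analyses will be carried out using SAS version 9.4 (or higher) statistical software". No procedure, sum-of-squares type, centring, least-squares-means statement or covariate value is named, and baseline cognition is not tied to a scale. The same paragraph separately plans secondary analyses that add covariates and examine their interactions with group.

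Section 3.0 lists one cognitive measure, the MoCA, taken at screening and week 24. In Section 8.1 the criterion "Screening MoCA" is set at 20 or above.

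Section 5.1 describes a single-arm cohort of 15. For the Nurr1 change it plans a comparison "which will be compared with the data from the three control PD patients from the pilot study using ANCOVA". It also plans ANCOVA for free water against the UF and PPMI cohorts. It lists no covariates and mentions no interaction. Section 19.2 gives no power analysis.

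**The concern.** When a continuous covariate interacts with group, there is no single group effect. The difference between groups is a function of the covariate, and the analyst has to say where on that function the test is made. Section 19.1 does not.

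One routine route is the Type III test of the group term with the covariate left on its raw scale. That tests the difference in intercepts, which here is the lithium effect at a MoCA of zero, at least 20 points below any eligible patient. A permutation reference distribution protects the size of this test but keeps the same statistic, so it recovers no power. Another routine route takes the contrast at the mean MoCA. That answers the right question but still fits a separate slope to each group, including a comparator of three patients.

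At stake is a real lithium effect being reported as null because of how the model was parameterised. Leaving the contrast open also lets it be chosen after the data are seen.

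**Working it through.** **The plan's own figure.** Section 5.1 states that two patients give 95% power at two-sided 0.05 for a 540% effect with SD 22%. The effect is 540/22 = 24.5 SD. The usual formula gives n per arm = 2 × (1.96 + 1.645)² × (22/540)² = 0.04, which rounds up to 1 per arm, or 2 in total. The figure reproduces, but it allows for no covariate or interaction.

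**Inputs.** From the documents: 15 treated patients; three pilot controls; PPMI n = 103 (pSN) and 130 (DMN-T, nbM) from Table 1; MoCA at least 20; two-sided alpha 0.05. Assumed, because the documents do not say: baseline cognition is a continuous MoCA with mean 25–27 and SD 1.5–3.5, limited to 20–30; common residual SD; no true interaction.

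**Formulas**, in residual-SD units, with S1 and S2 the within-group sums of squares of MoCA (means m1, m2):

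- Interaction model, contrast at MoCA = c: variance = 1/n1 + 1/n2 + (m1 − c)²/S1 + (m2 − c)²/S2, with n1 + n2 − 4 degrees of freedom.
- No interaction: variance = 1/n1 + 1/n2 + (m1 − m2)²/(S1 + S2), with n1 + n2 − 3 degrees of freedom.

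**Illustration.** Take 15 vs 3, both MoCA means 26 and both SDs 2.5, so S1 = 14 × 6.25 = 87.5 and S2 = 2 × 6.25 = 12.5.

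- No interaction: variance = 1/15 + 1/3 = 0.40, so SE = 0.63.
- Interaction, c = 0: variance = 0.40 + 676/87.5 + 676/12.5 = 0.40 + 7.73 + 54.08 = 62.2, so SE = 7.9.

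A 2-SD effect is 2/0.63 = 3.2 standard errors in the first case and 2/7.9 = 0.25 in the second. Over simulated MoCA values, the median SE ratio is about 12–25 for 15 vs 3 and about 12 for 15 vs 130 (MoCA SD 2.5).

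**Power**, from the noncentral t averaged over simulated MoCA values:

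| Comparison | Effect (SD) | At MoCA 0 | At mean MoCA | No interaction |
|---|---|---|---|---|
| 15 vs 3 | 1.90 | 0.05–0.06 | 0.63–0.64 | 0.77–0.78 |
| 15 vs 3 | 2.0 | about 0.05 | 0.67–0.69 | about 0.81 |
| 15 vs 3, stated Nurr1 effect | 24.5 | 0.36–0.70 | 1.00 | 1.00 |
| 15 vs 103 | 1.0 | about 0.06 | about 0.94 | about 0.95 |
| 15 vs 15, for reference | 1.06 | 0.05–0.06 | 0.78 | 0.79 |

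**Free water at the pilot effects** (Table 1, medium dose against PPMI one-year change, PPMI SD, MoCA SD 2.5):

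- DMN-T: |−0.0098 − 0.0100|/0.030 = 0.66 SD. Power is 0.06 at zero, 0.65 at the mean and 0.67 without the interaction.
- nbM: |−0.0416 − 0.0025|/0.041 = 1.08 SD. Power is 0.06, 0.97 and 0.97.
- pSN: |−0.0307 − 0.0180|/0.055 = 0.89 SD. Power is 0.06, 0.87 and 0.89.

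Halving the PPMI one-year change leaves power at zero between 0.05 and 0.06.

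**Permutation.** For 15 vs 3, all 816 relabellings were used (MoCA mean 26, SD 2.5). With no effect the rejection rate is 0.05 at either covariate value. At 1.9 SD, power is 0.04 at zero and 0.62 at the mean; at 2.4 SD, 0.03 and 0.79; at 24.5 SD, 0.54 and 1.00.

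**The case against.** A reader might infer that the plan's group test is the difference at a MoCA of zero and that its power therefore falls to alpha. The documents do not support that.

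- Section 19.1 names SAS and nothing more. The comparison at zero needs a continuous, uncentred covariate and a Type III group term, none of which is stated. The natural SAS tool for the planned pairwise comparisons, least-squares-means differences, uses the covariate mean by default. Centring, or sequential tests with group entered first, would also avoid the problem.
- MoCA as baseline cognition is an inference. Section 19.1 speaks of ANOVA, so a categorical cognition factor is possible, and then no extrapolation to zero arises.
- At the stated Nurr1 effect, power at zero is 0.36–0.70, well above alpha.
- Section 19.1 is written for three randomised groups, while the 15 vs 3 and PPMI comparisons come from Section 5.1, which says ANCOVA without an interaction. It is not settled which model will test lithium. Table 1 gives only summary data for UF and PPMI, and the documents do not say that patient-level MoCA is available.

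All of this stands and makes the worst case conditional. It does not remove the point. Section 5.1 names no terms, so it does not replace the only model specified. The contrast is undefined under every reading, and the favourable one still fits two parameters to three controls.

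The 24.5-SD figure also uses the SD of untreated controls. Section 4.1 gives four medium-dose patients, a mean increase of 679% and 75% responders (above 200%). If 679% is the mean of individual changes, one patient is at or below 200% and the other three average at least (4 × 679 − 200)/3 = 839%. The SD is then at least √[(479² + 3 × 160²)/3], about 319%. Against that spread, 540% is at most 540/319 = 1.7 SD, so effects near 2 SD are relevant to Nurr1 as well.

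**Conclusion.** The point holds in conditional form. Section 19.1 places the interaction in the main model for every outcome and leaves the tested contrast undefined. If the covariate is a raw-scale MoCA and the group term is tested by Type III, power is about 5–6% for a 2-SD effect (15 vs 3) or a 1-SD free-water effect (15 vs 103), against about 81% and 95% without the interaction. For the stated Nurr1 effect it is about 36–70%, below the stated 95%. If the contrast is taken at the mean MoCA, the cost is about 12–14 points with three controls at 2 SD and about 1 point against PPMI.

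These figures rest on the assumed MoCA distribution, a common residual SD and no true interaction. The documents do not show which contrast the analyst will use, so this is a specification gap with a severe worst case, not a demonstrated failure of the test.

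**What to change.** In Section 19.1, define the primary test for each outcome as the group effect in a main-effects ANCOVA with group and baseline cognition and no interaction, and name the MoCA as the covariate if that is what is meant. Move the group-by-cognition interaction to the secondary covariate analyses already described there, with MoCA centred at the sample mean so that the group term refers to an average enrolled patient.

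In Section 5.1, state that the Nurr1 and free-water ANCOVA comparisons use this same model. Reconcile the randomised three-group wording of Section 19.1 (group assignment, pairwise comparisons, randomisation distribution) with the single-arm cohort and its external comparators.

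This takes a few sentences and no new data collection from enrolled patients. The PPMI and UF comparisons need baseline cognition for those patients; if it cannot be obtained, the plan should say so and state the model used instead. The downside is that the interaction leaves the main model and is reported only as a secondary result. Centring alone, with the contrast named, would cure the comparison at zero but keep the moderate loss with three controls.
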